13.2 Reporting Adverse Events

All procedure-related and device-related AEs (non-serious) and all SAEs from the time of the first probe placement through study completion (Visit 14), or to the time of early withdrawal of the study, must be reported in the AE eCRF. The Investigator will evaluate the severity of the event and its relatedness to the registry device or procedure.

The Investigator is required to report all applicable non-serious AEs to the Sponsor within 2 weeks of becoming aware of the adverse event(s). All SAEs are to be reported as soon as possible, but no later than 72 hours after becoming aware of the event, regardless of relationship to the device or study procedure.

The study site will report applicable AEs and all SAEs to the Sponsor by entering the event into the EDC system via the Adverse Event eCRF, which will trigger an automated email to the Sponsor. Additional information, including the Investigator's assessment, may be added to the eCRF later. Any necessary medical management of the event will be recorded in the patient's medical record/source document. If the Sponsor requires supporting documentation or other information, the Sponsor will contact the study site.

Data related to AEs and SAEs will be collected until event resolution, until the event is considered stable, or until all attempts to determine the resolution of the event are exhausted. All AEs and SAEs that are unresolved at study completion (or early termination) will be recorded as ongoing at study end.

In addition, the following information should be recorded:

- Onset date
- Resolution date or date of death
- Action taken
- Event status (ongoing at registry end or resolved)
- Relationship of AE to the ablation device used in the registry
- Relationship of AE to the registry procedure
- Indication of seriousness.
- Was AE anticipated or not (only for serious, device-related AEs)

The report of an AE or SAE by a site does not constitute an admission that registry personnel or the user facility (hospital/clinic) caused or contributed to the event. The site is responsible for submitting AEs to the reviewing IRB/EC, per their IRB/EC procedures.

For retrospectively enrolled patients, the site should review patient medical records (i.e. through chart review) to look for reportable AEs/SAEs. Collection of AE data and reporting requirements will be the same for retrospective events, however, Sponsor reporting timelines do not apply.

13.3 Product Complaints

Product Complaint Definition

A product complaint is defined as any written, electronic, or oral communication that alleges deficiencies related to the identity, labeling, quality, durability, reliability, safety, effectiveness, or performance of a device after it is released for distribution (21CFR 820.3 (b)). A product complaint may or may not be associated with an AE/SAE.

Product complaints may include, but are not limited to:

- Product contamination;
- Defective components;
- Poor packaging or product mix-up;
- Device malfunction (the failure of a device to perform as intended for this registry);
- Labeling concerns;
- User errors.

Reporting Product Complaints

All product complaints related to devices in the procedure shall be documented throughout the registry study.

The registry site must report product complaints related to a device manufactured by NeuWave Medical, Inc., in a timely manner after becoming aware of the event. When any representative of the Sponsor becomes aware of a product complaint, the Sponsor representative must notify the Sponsor's Product Complaint Team with the least practical delay after becoming aware of the event through a Product Complaint Form to the following email address ([contact]) or by calling [name], Option 5.

One copy of the processed form should be kept on-site, and the device should be retained. Sponsor representatives will organize collection of the device for evaluation, as needed.

14.0 DEVIATIONS FROM THE CLINICAL REGISTRY PLAN

A protocol deviation is any noncompliance with the registry protocol, Good Clinical Practice, or protocol-specific requirements. A deviation (any activity conducted outside the parameters established by the registry protocol) can be identified from a number of sources. Potential sources include but are not limited to: a member of the Investigator's staff, a Sponsor representative during monitoring visits, or a member of the data management or statistical groups when entering or analyzing data. Regardless of the source, it is crucial to document the deviation in the protocol deviation eCRF. The Investigator will report protocol deviations to the IRB/EC as required by the IRB/EC procedures.

Any deviation from the protocol or procedures should be recorded in the source documents. Assessments or visits that are not completed because they are not SOC at a site, or assessments that were not completed for retrospective patients, should not be considered protocol deviations.

Steps to be taken to assure the accuracy and reliability of data include the selection of qualified investigators and appropriate sites, the review of protocol procedures with the Investigator and associated personnel prior to the registry, and periodic monitoring visits by the Sponsor. The Sponsor will review eCRFs for accuracy and completeness during monitoring visits; any discrepancies will be resolved with the Investigator or designees, as appropriate.

15.0 REGISTRY PRODUCT

All NEUWAVE Microwave Ablation Systems, the NEUWAVE Microwave Ablation System with Ablation Confirmation, and the NEUWAVE Ablation Probes used in the registry are legally marketed in the countries where they are used. The registry products should be used within their cleared indications as per the Instructions For Use.

16.0 CLINICAL MONITORING

This registry will be monitored by the Sponsor to ensure the following:

- The rights and well-being of the patients are protected.
- Reported registry data is accurate, complete, and verifiable from source documents.
- The conduct of the registry is in compliance with the currently approved protocol/amendment(s), applicable GCPs, and with applicable local regulatory requirements.

Steps to be taken to assure the accuracy and reliability of data include the selection of qualified investigators and appropriate sites, review of protocol procedures with the Investigator and associated personnel prior to the registry, and periodic monitoring visits by the Sponsor. The Sponsor will review eCRFs for accuracy and completeness during monitoring visits; any discrepancies will be resolved with the Investigator or designees, as appropriate.

The extent and nature of monitoring will be predetermined and based on considerations such as the objective, design, complexity, and endpoints of the registry and mutually agreed to by the Sponsor and investigators. Monitors will comply with established written standard operating procedures as well as procedures (i.e., monitoring plan) specified by the Sponsor for monitoring this registry. These monitoring procedures are characterized in the Monitoring Plan for this registry.

17.0 STATISTICAL METHODOLOGY

17.1 Statistical and Analytical Plans

The Sponsor Data Management and Biostatistics groups will be responsible for the analysis of data from this protocol. A comprehensive and detailed Statistical Analysis Plan (SAP) to supplement the statistical design and analysis described in this section will be finalized prior to the first analysis of data from this protocol.

Categorical variables will be summarized descriptively by frequencies and associated percentages. Continuous variables will be summarized descriptively by number of patients, mean, standard deviation, median, minimum, and maximum. Confidence intervals will also be provided for procedure-related variables.

17.2 Registry Design

This is a multicenter, observational registry that follows patients for a total of up to 5 years from the date of the first liver ablation procedure with either the NEUWAVE Microwave Ablation System or the NEUWAVE Microwave Ablation System with Ablation Confirmation.

This is an “umbrella registry,” which was included as an optional component in other NEUWAVE studies; hence, data from consenting patients who are or will be enrolled in other NEUWAVE soft tissue liver lesion ablation studies will be included in this registry. All other patients will be enrolled and followed prospectively, enrolled retrospectively with prospective, longitudinal follow up, or enrolled retrospectively with all retrospective follow up.

17.3 Treatment Assignment

This is a single-arm registry where all enrolled patients will be ablated using the NEUWAVE Microwave Ablation System as part of the site’s SOC treatment or per protocol for those patients who are also enrolled in other NEUWAVE studies.

17.4 Interval Windows

Interval windows are provided in the Schedule of Assessments, which appears at the end of the Protocol Summary. No additional windows are planned for analysis purposes.

17.5 Primary Endpoint and Associated Hypotheses

This protocol does not have a single primary endpoint and there are no associated hypotheses. Rather, there are several patient-level outcomes of interest that will be investigated through statistical modeling to estimate the relationship between these outcomes and various patient, provider, and ablation-specific parameters. These patient-level outcomes of interest include: technical success, technique efficacy, secondary efficacy rate, target lesion recurrence rate, recurrence-free survival, and overall survival.

17.6 Levels of Significance

No levels of significance are specified as no specific hypotheses about any of the outcomes of interest are being formulated or tested. Significance levels relating to variable selection in a statistical regression model will be specified in the SAP.

17.7 Analysis Sets

All patients contributing data to the registry will be considered eligible for inclusion into planned analyses. Specific rules regarding a minimum or critical number of observed dependent and independent variables for inclusion into statistical modeling analyses will be specified in the SAP.

17.8 Sample Size Justification

This registry will be open to receiving data from all patients who are ablated with microwave ablation of soft tissue liver lesions using the NEUWAVE Microwave Ablation System. Given that the objective of the registry is to investigate the relationships that exist between the stated clinical outcomes, patient and provider parameters, and microwave ablation (MWA) time and power, no power analysis or sample size determination have been performed given the absence of a specific hypothesis to test. Rather, a statistical modeling exercise will occur at pre-specified intervals after sufficient data has been entered to support exploratory statistical modeling. The timing of these analyses will be defined in the SAP. Additional ad-hoc analyses will be conducted throughout the duration of the registry.

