1.1 Study objective

1.1.1 Primary Objective

The primary objective of this registry is to compile data that will be analyzed at various timepoints, to understand the impact of selected parameters on procedure and patient outcomes. The database will capture data related to (1) Ablation Procedure parameters, (2) Patient parameters, and (3) Healthcare Provider parameters.

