8.6.1 Plans for Interim Analysis

There are no plans for interim analyses with an intent to stop the registry early or to adapt the registry design or planned number of patients.

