8.6.2 Plans for Final Analysis

Final analysis will be conducted after the database lock takes place for the study.

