8.7 Sensitivity Analyses

No sensitivity analysis will be conducted.

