8.10 Exploratory Analyses

Logistic regression analysis will be utilized to explore the relationship between dichotomous clinical outcomes (technical success and technique efficacy) and ablation procedure, patient, and provider parameters. Significance level of 0.2 will be used for variable selection in a regression model. Cox proportional hazard model will be used for time to event analyses for target lesion recurrence to explore the relationship with ablation procedure, patient, and provider parameters.

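### The SAP's exploratory models for ablation guidance have no internal validation, and the modelling timing that the protocol leaves to the SAP is not given there

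*Protocol*

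**What the plan says.** **Purpose.** The protocol's title and section 7.1 give the aim as developing ablation parameter guidance. SAP 1.1.1 states the objective as to "compile data that will be analyzed at various timepoints, to understand the impact of selected parameters on procedure and patient outcomes".

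**Models.** SAP 8.10, headed as exploratory, plans logistic regression for technical success and technique efficacy on procedure, patient and provider parameters, and a Cox model for target lesion recurrence. On selection it says: "Significance level of 0.2 will be used for variable selection in a regression model". It gives no candidate list, direction of selection or performance measure, and does not say whether the level also governs the Cox model. Neither document mentions a hold-out sample, cross-validation, bootstrap, discrimination or calibration. SAP 8.7 ("No sensitivity analysis will be conducted") and 8.14 (no additional endpoint analyses) supply nothing of the kind. The central review in protocol 11.3 compares image readings; it does not test a model.

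**Timing.** Protocol 17.8 says that "a statistical modeling exercise will occur at pre-specified intervals after sufficient data has been entered to support exploratory statistical modeling", and continues: "The timing of these analyses will be defined in the SAP. Additional ad-hoc analyses will be conducted throughout the duration of the registry". SAP section 7 carries over the sample size text from 17.8 without those sentences. SAP 8.6.2 says only: "Final analysis will be conducted after the database lock takes place for the study".

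**The concern.** A model whose terms are chosen and judged on the same patients keeps chance associations and overstates the real ones. A lenient level, a long candidate list and few failures all make this worse. A reader who takes power, time or probe settings from such a model as guidance has no way to tell how much of the fit would survive in the next patients. The plan provides no figure that would show it.

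The timing gap is a smaller and separate matter. The protocol hands a decision to the SAP and the SAP does not take it, so the two documents describe different analysis programmes.

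**Working it through.** **No figure to reproduce.** The documents state no power, event rate or model performance.

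**Inputs from the documents**
- Patients: 1,500 (protocol summary, up to; section 7.2, at least).
- Listed parameters in protocol 19.1: 25 procedure (a to y) + 22 patient (8 lesion + 7 history + 3 family and genetic + 4 exposure) + 1 provider = 48. Laboratory values, ECOG and demographics are extra. Not every item would serve as a predictor. Protocol 17.9 leaves data reduction to the SAP, which specifies none. So 48 stands for an unreduced list and 20 is an assumed shorter one.
- Selection level: 0.2 (SAP 8.10).

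**Assumptions not in the documents**
- Failure rate 2%, 5% or 10%.
- Independent, standard normal candidates.
- Backward elimination.
- Complete data.
- Either no true predictor, or three with an odds ratio of 1.5 per SD.

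**Information per candidate.** Failures = 1,500 × rate = 30, 75 or 150. Per candidate this is 30/48 = 0.6, 75/48 = 1.6 or 150/48 = 3.1. With 20 candidates it is 1.5, 3.8 or 7.5.

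**Expected chance selections if nothing matters.** 48 × 0.2 = 9.6, or 20 × 0.2 = 4.0.

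**Simulation.** Each data set of 1,500 was fitted by backward logistic regression at 0.2. The final model was scored on the same patients (apparent) and on 20,000 new ones. There were 60 replicates per row. The calibration slope is the coefficient from regressing the new outcomes on the model's linear predictor.

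| Failure rate | Candidates | Three true predictors: apparent AUC | New AUC | Slope | No true predictor: apparent AUC | New AUC |
|---|---|---|---|---|---|---|
| 2% | 20 | 0.75 | 0.63 | 0.50 | 0.68 | 0.50 |
| 2% | 48 | 0.82 | 0.60 | 0.26 | 0.77 | 0.50 |
| 5% | 20 | 0.72 | 0.66 | 0.70 | 0.61 | 0.50 |
| 5% | 48 | 0.75 | 0.63 | 0.48 | 0.68 | 0.50 |
| 10% | 20 | 0.71 | 0.67 | 0.81 | 0.58 | 0.50 |
| 10% | 48 | 0.72 | 0.65 | 0.64 | 0.63 | 0.50 |

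A repeat of the 5% and 10% rows with 100 replicates and another seed agreed to within 0.01 on AUC and 0.03 on slope.

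**Reading the slopes.** The spread of predicted log-odds is too wide by a factor of 1/slope. At 5% and 10% failures that runs from 1/0.81 = 1.2 to 1/0.48 = 2.1.

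**Timing, side by side**

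| Question | Protocol | SAP |
|---|---|---|
| When is modelling done? | At pre-specified intervals, timing left to the SAP (17.8) | After database lock only (8.6.2) |
| Interims to stop or adapt? | None (17.9) | None (8.6.1) |
| Ad-hoc analyses? | Throughout (17.8) | Not mentioned |

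SAP 8.6.1 rules out only interims meant to stop or adapt the registry. It neither schedules nor forbids interval modelling.

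**The case against.** **Validation was never promised.** The models are labelled exploratory, there are no hypotheses, and no c-statistic is planned, so no inflated one is promised for reporting. This stands: the omission breaks no commitment. But the exploratory label does not make in-sample effects fit for guidance, and exaggerated coefficients do harm even if no c-statistic is printed.

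**The simulation is stylised.** Real parameters are correlated, many are collected only if available, and SAP 8.11 imputes nothing. The selection direction is assumed. The case with no true predictor is an extreme, and the mildest row shows a gap of only 0.71 − 0.67 = 0.04. This stands as a limit on the size, not on the direction.

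**A reader might infer that interim guidance will come from unplanned looks.** No section says that guidance will be issued before the final analysis. Protocol 17.1 requires the SAP to be final before the first analysis, and the SAP is dated 30 Oct 2025. The documents do not show whether any interval modelling has taken place.

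**A reader might infer that the primary objective goes unmet.** The phrase "compile data that will be analyzed at various timepoints" can mean outcome timepoints: protocol 6.2 orders the primary endpoints by time, and SAP 8.5 estimates recurrence from 3 to 60 months.

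**A reader might infer inflation from repeated testing.** The SAP plans one analysis, which is sound in itself, and neither document gives a number of looks. SAP 8.1 also requires final analyses that depart from the plan to be identified in the output and documented in the study report. That partly covers the labelling of ad-hoc work.

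**Conclusion.** The point holds in two parts of unequal weight.

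1. **No internal validation.** This is a gap against the registry's stated aim, and cheap to close. With three true predictors and 5% or 10% failures, apparent AUC exceeds new-patient AUC by about 0.04 to 0.12, with slopes of 0.48 to 0.81. At 2% failures the excess is 0.12 to 0.22 (0.75 − 0.63 and 0.82 − 0.60), with slopes of 0.26 to 0.50. With no true predictor, apparent AUC is 0.58 to 0.77 against 0.50. These figures rest on the assumptions listed and apply to the logistic models. No figure was derived for the Cox model, which has the same gap.
2. **Missing timing.** Protocol 17.8 commits the SAP to define when interval modelling occurs and the SAP does not. This is a mismatch to reconcile. It does not show that the final analysis is unsound or that any guidance has come from unplanned looks.

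**What to change.** **SAP 8.10.** For each final logistic and Cox model, bootstrap the whole modelling procedure, with variable selection repeated in every resample. Resample patients (or sites) as clusters, because a patient may contribute several lesions. Optimism is the mean over resamples of (performance in the resample − performance of that resample's model in the full data), and corrected performance = apparent − optimism. Report the corrected c-statistic and calibration slope, and how often each parameter is selected. State the candidate list and selection direction, since the bootstrap cannot be programmed without them.

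**Protocol 17.8 and SAP 8.6.1 to 8.6.2.** Either list the modelling timepoints or data triggers in the SAP, or withdraw the protocol sentence. Label any other analysis as ad hoc.

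**Cost.** SAP wording (and protocol wording, if the sentence is withdrawn) and some programming. Reported performance will be less favourable. No new data and no burden on patients.

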17.9 Analyses to be Conducted

Categorical variables will be summarized descriptively by frequencies and associated percentages. Continuous variables will be summarized descriptively by number of patients, mean, standard deviation, median, minimum, and maximum. Confidence intervals will also be provided for procedure-related variables.

Disposition of Registry Patients

Patient disposition will be summarized using counts and percentages. The number and percentage of patients completed and discontinued along with the specific reasons for discontinuation will be tabulated.

Demographic and Baseline Characteristics

Summary statistics will be provided for patient demographics and pre-operative ablation characteristics.

Primary and Secondary Endpoint Analyses

Regression analysis methodologies will be utilized to explore the relationship between dichotomous clinical outcomes (technical success, technique efficacy, and secondary efficacy rate) and ablation procedure, patient, and provider parameters. Time to event analyses will be used for target lesion recurrence, regional recurrence rate, recurrence-free survival, progression free survival, and overall survival.

Complete details regarding all analysis methodologies including approaches to handle multiple lesions per patient, variable selection techniques, data reduction techniques given the number of potential independent variables, as well as subgroup analyses of interest will be specified in the SAP.

The number and percentage of patients achieving technical success will be summarized and a 95% confidence interval will be provided. A similar summary will be provided for technique efficacy, as well as for the primary and secondary efficacy rates, as previously defined.

Target lesion recurrence rates at each post-ablation scheduled visit will be estimated using the Kaplan-Meier method and 95% confidence intervals will be provided. A similar summary will be provided for the 5-year overall rate. Similar summaries will also be provided for regional recurrence rate, overall and progression-free survival rates for the entire observation period from the ablation procedure date through 5 years of follow-up.

Scores from the EORTC QOL questionnaires and Numeric Pain Rating Scales will be summarized with methodology consistent to the recommendations of the specific survey. Additional endpoints will be summarized with descriptive statistics.

Plans for Interim Analysis

There are no plans for interim analyses with an intent to stop the registry early or to adapt the registry design or planned number of patients.

Analysis of Safety

From start of ablation procedure through the 5-year follow-up visit, procedure and device-related AEs, and all SAEs will be collected, and these will be summarized by system organ class and preferred term. Ninety-five percent confidence intervals may be provided for pre-specified adverse events of interest, which are:

- Ascites (accumulation of fluid causing abdominal swelling)
- Biloma/bile leak (buildup of bile within the abdomen)/bile leak)
- Bile duct injury
- Bleeding requiring transfusion, embolization (obstructing of blood vessel or organ to stop bleeding), or prolonged hospital stay
- Intrahepatic hematoma
- Pneumothorax and hemothorax
- Organ injury other than the liver (such as gastrointestinal injury/perforation, diaphragmatic injuries/hernia)
- Fever
- General feeling of tiredness
- Infection

- Liver dysfunction.
- Liver abscess
- Nausea
- Pain
- Pneumonia
- Pleural effusion
- Post ablation syndrome, which is your body's response to the destroyed lesion. You may experience flu-like symptoms, including fever, decreased appetite, and general discomfort. This syndrome generally happens 3 to 5 days after the ablation procedure.
- Skin burn
- Thrombosis (local coagulation or clotting of the blood in the circulatory system, with/without tube drainage)
- Tumor implantation

Handling of Dropouts or Missing Data

Given that this is a registry that will include both retrospective and prospective data, with some patients coming from other NeuWave clinical trials, missing data is expected for both the dependent and independent variables in the regression analyses described above. Specific rules regarding imputation of missing data (e.g. multiple imputation, minimum number of observed variables, sensitivity analyses) will be provided in the SAP.

Multicenter Studies

Analyses will be adjusted for center through the inclusion of the various provider-specific variables described above.

Analysis of Subgroups

Subgroup analyses will be performed for levels of the following variables: Location of lesion (near vessel >3mm, Dome, Subcapsular, Segment); Underlying disease (mild, moderate or severe cirrhosis; presence of fatty liver; post chemotherapy); Type of disease (CRLM, HCC, Cholangiocarcinoma, Other); ASA score; Child-Pugh score; Type of hospital; Experience of the ablationist; AC vs no AC; and gender. Additional subgroups of interest may be identified pending the distribution of various parameters at enrollment. Details regarding the analysis methodologies for these subgroups will be pre-specified in the SAP.

